## A. STUDY BACKGROUND AND PURPOSE

Under-immunization rates for childhood immunizations in the United States ranges from 8-20%. Previous studies have demonstrated that pediatric patients are most likely to be under-immunized for seasonal immunizations. The aim of this study is to explore the factors and facilitators contributing to measles immunization hesitancy. Secondly, we aim to explore the impact of hypothetical contexts on measles immunization hesitancy. The results of this study may identify potential disparities in measles immunization coverage and potential solutions for resolving those disparities.

## B. STUDY DESIGN

This will be a cross sectional RCT study conducted through web-based surveys to determine factors and facilitators contributing to measles immunization confidence in the ED.

*Aim 1: Identify the characteristics of the measles under-immunized population.* Parents of patients aged 1 year up to and including 6 years of age who present to the AMC pediatric ED between 6/1/2025 and 6/1/2026 will be screened for the below exclusion criteria:

- The patient is critically ill- Any life-threatening condition that requires pharmacological and/or mechanical support of vital organ functions, i.e. shock, moderate to severe asthma exacerbation, airway obstruction, anaphylaxis, etc.
- The patient presents with major (i.e. leveled) trauma
- The patient presents with concern for physical or sexual assault
- The patient presents with need for child protective service evaluation
- The patient or guardian are not English speaking
- The patient presents in custody of a juvenile detention center or law enforcement
- The patient presents without a consenting parent or legal guardian present at time of evaluation

Parents of children meeting the above inclusion and exclusion criteria will be approached for consent to participate in the study by convenience sampling weekdays 0900-1700. All consenting guardians will complete a brief survey to assess parental demographics and child immunization history. The below questions will be included in the brief survey:

- Age of caregiver
- Age of child
- Race of caregiver
- Ethnicity of caregiver
- Education level of caregiver
  - High school degree
  - College/University/technical school degree
  - Post-graduate college/university degree
- Household income level of caregiver
  - <24,000
  - 24,001-53,000
  - 53,001-89,000
  - 89,001-136,000
  - ≥136,001
  - Unknown
- What source do you find to be the most effective at communicating vaccine information
  - Social media
  - PCP (Primary care physician)

- Personal communication with friends/families
- Government agencies (i.e. Center for Disease Control and Prevention)
- Pharmaceutical companies
- On average, how many minutes do you (the guardian) spend on social media outlets per day?
  - 0-30 minutes
  - 31-60 minutes
  - 61-120 minutes
  - 121-180 minutes
  - 181-240 minutes
  - ≥241 minutes
- Is your child up to date with all routine (Not including influenza, COVID-19, RSV) immunizations at this time?
- Is your child immunized against Influenza for this season?
- Is your child immunized against COVID-19 for this season?
- Is your child immunized against RSV for this season?
  - Yes, the mother was immunized for RSV during pregnancy.
  - Yes, the child was immunized for RSV as an infant.
  - No
  - Unsure

All participants who identify that their child is under-immunized for measles (i.e. did not receive 1st MMR immunization at 1 year of age OR 2nd MMR immunization at 4 years of age) will go on to complete a comprehensive survey to assess immunization beliefs, to include:

- Please indicate that you agree or disagree with the below statements when thinking about getting your child up to date with all of their recommended immunizations?
  - Receiving all the recommended vaccines would significantly reduce my child's risk of getting sick (Vaccine Efficacy)
    - Agree or Disagree
  - Receiving all the recommended vaccines would be safe for my child (Vaccine Safety)
    - Agree or Disagree
  - Receiving all the recommended vaccines would be like performing an experiment on them (Vaccine Distrust)
    - Agree or Disagree
  - Receiving all the recommended vaccine will lead to long-term health problems for my child (Vaccine Long-Term Health Problems)
    - Agree or Disagree
  - Receiving all the recommended vaccines would be harmful to my child because of their current medical condition (Child's Medical Condition)
    - Agree or Disagree

- Agree or Disagree
- Receiving all the recommended vaccines is unnecessary because there is less risk now that young children will be infected with the virus or bacteria (Low Risk of Infection)
  - Agree or Disagree
- Receiving all the recommended vaccines is unnecessary because America has reached herd immunity for the virus or bacteria (low risk for infection)
  - Agree or Disagree
- The opinion of my child's doctor or healthcare provider will influence my decision about getting my young child vaccinated (Not recommended by Provider)
  - Agree or Disagree
- Getting children vaccinated against infectious diseases supports the community by stopping the spread of the disease among other children and adults (Stopping Community Spread)
  - Agree or Disagree
- I do not have enough information about all the recommended vaccines to be comfortable giving them to my child (lack of information)
  - Agree or Disagree
- I do not have a health care provider who has offered my child the vaccine (lack of healthcare access)
  - Agree or Disagree
- I cannot miss work (have my child miss school) for a doctor's appointment to receive the vaccine (Social barriers)
  - Agree or Disagree
- I do not have transportation to get my child to the doctor's appointment to receive the vaccine (social barriers)
  - Agree or Disagree

– “Do you plan to get your child fully immunized for measles?”

- “Definitely not”
  - “Probably not”
  - “Unsure”
  - “Yes”

*Aim 2: Explore the impact of favorable immunization messaging on parental confidence in the measles in the under-immunized population.*

All guardians who complete the comprehensive survey will be randomized to receive one of four patient-centered immunization messages. The guardian will then be asked again if they plan to immunize their child against RSV this season and if they would accept the immunization if we administer it at the current visit.

- “Would you give your child the measles vaccination at this visit. This vaccine is known to prevent pneumonia that could lead to death and brain swelling that could lead to seizures or deafness?”
  - “Definitely not”
  - “Probably not”
  - “Unsure”
  - “Yes”
- “Would you give your child the measles immunization at this visit. This immunization is known to prevent pneumonia that could lead to death and brain swelling that could lead to seizures or deafness?”
  - “Definitely not”
  - “Probably not”
  - “Unsure”
  - “Yes”
- “Would you give your child the measles shot at this visit. This shot is known to prevent pneumonia that could lead to death and brain swelling that could lead to seizures or deafness?”
  - “Definitely not”
  - “Probably not”
  - “Unsure”
  - “Yes”
- “Would you give your child the measles medicine at this visit. This medicine is known to prevent pneumonia that could lead to death and brain swelling that could lead to seizures or deafness?”
  - “Definitely not”
  - “Probably not”
  - “Unsure”
  - “Yes”

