### **D. DATA ANALYSIS**

We will collect the following data: Age, Gender, Race, Ethnicity, State of residence, parental age, parental education level, household income, insurance status, parental report of immunization status and the reason for under-immunization if applicable. The sub-investigators will perform the data analysis at Albany Medical Center (AMC) with an AMC approved password protected PC. Storage of files will be on a password protected departmental drive. Use of a password protected master key document to store identifiers separately from other study variables, which will be collected and stored through REDCAPs.

Our primary outcome is the demographic variables and immunization beliefs that are associated with RSV under-immunization. Survey responses will be used to stratify outcomes according to child's age, Gender, Race, Ethnicity, State of residence, parental age, parental education level, household income, insurance status, and sources of health information. The secondary outcome is the improvement in immunization confidence (defined as converting from "definitely not intent, unsure about intent, or probably not intent" to "intent") stratified by patient-centered immunization messaging.

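### The caregiver education item has no option below a high school degree, so a planned stratifier cannot show the least-educated caregivers

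*Protocol*

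**What the plan says.** Protocol section B (Aim 1) lists the questions of the brief survey. One is "Education level of caregiver", with three response options:

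- "High school degree"
- "College/University/technical school degree"
- "Post-graduate college/university degree"

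Nothing sits below the first option, and there is no other, none or unknown choice. The next item, household income, has an open bottom band and an unknown option.

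The survey goes to everyone who consents: "All consenting guardians will complete a brief survey to assess parental demographics and child immunization history". None of the seven exclusion criteria concerns the caregiver's schooling.

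Section D makes demographic variables associated with under-immunization part of the primary outcome. It will stratify outcomes by a list that includes "parental education level, household income, insurance status, and sources of health information". Section A says the results "may identify potential disparities in measles immunization coverage".

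**The concern.** The response list does not cover the eligible population. A caregiver who did not finish high school has no truthful answer. That caregiver will either choose the high school option, which then mixes two groups, or leave the item blank, in which case missingness depends on the value that is missing.

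Either way the bottom of the education gradient cannot be seen, in a study whose first aim is to describe who is under-immunized. A statistical analysis plan cannot correct this, because the distinction is lost when the answer is recorded. The chart variables listed under Patient recruitment, enrollment, and progress through the study (race/ethnicity, gender, ESI level, insurance status, chief complaints) do not include caregiver education, so no stated source could restore it.

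**Working it through.** The protocol gives no figure on this point to reproduce. The check is a reading of the option list, followed by arithmetic on assumed values to show scale.

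**Is the list exhaustive for those asked?**

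- Lowest option: a high school degree (section B).
- Catch-all option: none (section B).
- Minimum schooling for eligibility: none (section B exclusions).
- Who answers: all consenting guardians (section B).
- Use: stratifier of outcomes (section D).

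Caregivers without a degree can be enrolled, will be asked, and have no valid answer.

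**How many could be affected?** Planned enrolment is about 800 (Sample Size Considerations). The share *s* without a high school degree is not in the protocol; assume 5% to 15%.

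- 0.05 × 800 = 40
- 0.15 × 800 = 120

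**What happens if they choose the high school option?** Assume that true high school graduates are 35% of the sample, with under-immunization of 15% in their children and 30% in children of caregivers without a degree. The reported rate in the merged stratum is

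(*s* × 0.30 + 0.35 × 0.15) / (*s* + 0.35)

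| *s* | Calculation | Reported rate | Shift from 15% | Merged stratum (of 800) |
|---|---|---|---|---|
| 0.05 | 0.0675 / 0.40 | 16.9% | 1.9 points | 320 |
| 0.10 | 0.0825 / 0.45 | 18.3% | 3.3 points | 360 |
| 0.15 | 0.0975 / 0.50 | 19.5% | 4.5 points | 400 |

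A milder set of assumptions has the same effect. With 240 high school caregivers at 12% and 80 below high school at 20%, the merged rate is (28.8 + 16) / 320 = 14%, and the 20% group is hidden.

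**What happens if they skip the item?** The high school stratum keeps its 15%, but education is missing for 5-15% of the sample, and those missing are the group of interest.

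**Income bands.** The lowest band is below 24,000 and the next starts at 24,001. A household at exactly 24,000 has no band. This is a much smaller fault of the same kind.

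**The case against.** **The printed list may not be the whole instrument.** The protocol refers to a separate data collection form that is not shown. It also omits response options for race and ethnicity, prints no MMR question although participants are routed on MMR status, and lists state of residence in section D without asking for it in section B. The fielded form may already have a lower category. This limits what can be said about the survey in use. It does not clear the protocol, which introduces its list as the survey questions and spells out the education options. If the form differs, the two must be aligned.

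**The magnitudes are assumed.** This is true. The 30% rate lies above the only background range given (8-20%, section A), and requiring English, written consent and a tablet survey could lower the share without a degree. The defect itself does not depend on these values.

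**The distortion is modest.** On the assumptions above, the 95% half-width in the merged stratum is about 4 points (1.96 × √(0.169 × 0.831 / 320) = 4.1 points), so two of the three shifts are within sampling error. If everyone affected picks the lowest option, it works as high school or less, which is coarser but still ordered. That is fair, but nothing in the plan makes caregivers answer that way, and the loss of the lowest group remains.

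**A separate stratum would be thin.** At a 30% rate, 40 to 120 caregivers give 12 to 36 under-immunized children. At the background 8-20% (64 to 160 of 800), 5-15% of those gives about 3 to 24. Associations with beliefs in so small a group would be imprecise. Even so, categories collected separately can be pooled later, and categories collected together cannot be split.

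**The scope is limited.** Education is one of about ten stratifiers in a convenience sample, and the randomized comparison of four messages is not invalidated. This stands and limits the weight of the point.

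**Conclusion.** The concern holds. As written, the education item has no truthful answer for caregivers without a high school degree, although they are eligible and education is a named stratifier in a study with a disparities purpose. They will be misclassified or missing, and analysis cannot recover the distinction.

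At an assumed 5-15% of 800, 40 to 120 caregivers are affected. Under the assumed 30% and 15% rates and a 35% high school share, the merged stratum would report 17-20%. These figures only illustrate scale; the conclusion rests on the option list, the eligibility criteria and section D. The harm is to Aim 1 and to any education-stratified result. It should be corrected, but it does not threaten the randomized comparison. The income gap at exactly 24,000 is real but trivial.

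**What to change.** In Protocol section B and the survey form, add *Less than high school degree* and *Prefer not to answer/unknown* to the education item. In the same edit, change the lowest income band to 24,000 or less so that it meets the next band. First check the fielded form: if it already has a lower category, correct the protocol to match it.

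The cost is a short REDCap edit and a minor amendment. Caregivers enrolled before the edit stay in the old categories, so each week of delay adds records that cannot be corrected. The analysis should distinguish answers given before and after the change.

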### **Sample Size Considerations**

We plan to enroll ~800 patients at AMC.

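### The RSV item asks about the current season, but its only 'Yes' answers are events in pregnancy or infancy, so at ages 1 to 6 it cannot be read as current-season RSV status

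*Protocol*

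**What the plan says.** Protocol section B (Aim 1) recruits "Parents of patients aged 1 year up to and including 6 years of age" who "present to the AMC pediatric ED between 6/1/2025 and 6/1/2026". Every consenting guardian completes the brief survey.

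Its RSV question is "Is your child immunized against RSV for this season". Four answers are listed: "Yes, the mother was immunized for RSV during pregnancy", "Yes, the child was immunized for RSV as an infant", 'No' and 'Unsure'. No answer covers a dose given after infancy, no RSV dose date is among the listed items, and the season is not defined. The influenza and COVID-19 questions also refer to the season, but they list no answers tied to an earlier period of life.

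Section D states: "Our primary outcome is the demographic variables and immunization beliefs that are associated with RSV under-immunization". The purpose in section A, both aims, the criterion for going on to the comprehensive survey and all four randomized messages concern measles.

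**The concern.** The question and its answers refer to different times. The question asks about the present season. The two affirmative answers describe events before birth or in the first year of life. In a sample that starts at the first birthday, those events are nearly always in the past.

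A guardian whose child had such an event has two defensible answers. One is to tick the 'Yes' that describes what happened. The other is to take the question literally and tick 'No' because nothing was given this season. Which answer is recorded then depends on the guardian's reading as well as on the child's history.

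At stake is the meaning of any RSV coverage figure from the survey, and of any association with it. If guardians of different education or age tend to read the question differently, that difference would appear as an association with RSV status.

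**Working it through.** The protocol gives no figure for this item, so there is nothing to reproduce. The check is one of timing.

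**Inputs from the protocol.** Age at interview *a* runs from 12 to under 84 months (section B, ages 1 to 6 inclusive). The 'Yes' events are before birth, or in infancy (read as before 12 months of age).

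**Assumptions, because the protocol is silent.** The season has length *L* = 5, 6 or 12 months. The interview falls *t* months after season start, with *t* uniform on 0 to *L*. Ages are uniform over the 72-month range. An infant dose is equally likely at any time in the first 12 months.

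**Step 1, pregnancy answer.** The latest possible date is birth, *a* months ago. It falls in the current season only if *a* < *t*. Since *a* ≥ 12 and *t* ≤ 12, the share is 0% for any season of 12 months or less. This step does not depend on the age mix.

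**Step 2, infancy answer, ages 2 to 6.** Infancy ended *a* − 12 months ago, which is at least 12 months for every child from the second birthday. This also holds for any age mix.

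**Step 3, infancy answer, whole age range.** Some part of infancy overlaps the season if *a* − 12 < *t*. With uniform ages the share is (*L*/2)/72:
- *L* = 5: 2.5/72 = 3.5%
- *L* = 6: 3/72 = 4.2%
- *L* = 12: 6/72 = 8.3%

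The dose itself falls in the season if the time since the dose is below *t*. That share is *L*²/(6 × 72 × 12) = *L*²/5184:
- *L* = 5: 25/5184 = 0.5%
- *L* = 6: 36/5184 = 0.7%
- *L* = 12: 144/5184 = 2.8%

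**Step 4, one-year-olds alone.** Replace 72 by 12:
- Overlap is (*L*/2)/12 = 20.8%, 25.0% and 50.0%.
- Dose in season is *L*²/864 = 2.9%, 4.2% and 16.7%.

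A younger sample therefore raises the share, but even among one-year-olds most infant doses fall before the current season. These are shares of children supposing that each had an infant dose. They are not shares of observed 'Yes' answers.

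**Step 5, what can be recovered.** Let *p* be the proportion with a pregnancy or infancy event, and *q* the proportion of those whose guardian ticks 'No' because of the season wording. Leaving 'Unsure' aside, and supposing that guardians of children without such an event tick 'No':
- observed 'Yes' = *p*(1 − *q*)
- observed 'No' = (1 − *p*) + *pq*

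The two shares add to 1, so they give one equation in two unknowns. Neither *p* nor *q* can be found. The 'Yes' answers name the route, and child age is collected, so they can be relabelled as past events. The 'No' answers cannot be split.

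**The case against.** The strongest objection concerns the word 'for'. The item asks whether the child is immunized for the season, not whether a dose was given during it. If an earlier exposure still counts, a 'Yes' from pregnancy or infancy is not false. The protocol does not say how long an exposure counts, and this review takes no position on that. This part of the objection stands. A reader might infer that every pregnancy 'Yes' is a wrong answer. The documents show only that the event was earlier.

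Second, much of the data is recoverable. The two routes are separate answers, child age is recorded, and the protocol nowhere says that the routes will be pooled and coded as current coverage. This also stands for the 'Yes' answers. It does not help with a 'No' prompted by the season wording.

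Third, a reader might attach a size to the problem. Ages 2 to 6 are 5 of 6 age-years, or 83%. If 5% to 40% of the planned 800 guardians ticked 'Yes', that would be 40 to 320 children (800 × 0.05 and 800 × 0.40), most of them misrecorded. The documents do not support this. The 5% to 40% is a free assumption. The 83% describes all eligible children under uniform ages, and it carries over to those answering 'Yes' only if 'Yes' is unrelated to age. Infancy answers may well cluster in one-year-olds.

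Fourth, the item may be only background. Entry to the comprehensive survey, and hence randomization, depends on measles status alone. This stands, and it limits the weight of the point.

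**Conclusion.** The point holds in a limited form. For ages 1 to 6, the pregnancy answer always describes an event at least 12 months before interview. The infancy answer does so for every child aged 2 to 6. Those two statements rest only on the protocol's age range and on reading infancy as the first year of life. Only some one-year-olds could have had an infant dose in the current season. With the uniform-age and dose-timing assumptions above, that is about 0.5% to 2.8% of all eligible children and 2.9% to 16.7% of one-year-olds.

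The item therefore cannot be read as current-season RSV status, and its 'No' answers mix never immunized with immunized in the past. The number of guardians affected cannot be derived from the protocol.

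A reader might infer that the primary outcome is invalid. That goes too far. The item bears on the primary outcome only if "immunization beliefs that are associated with RSV under-immunization" in section D is meant as printed. That wording conflicts with the measles aims, and the two must be reconciled as a separate matter. If section D is corrected to measles, the item affects only the RSV entry in the child's immunization history. Severity is minor to moderate.

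**What to change.** Reword the question to ask whether the child was ever immunized against RSV. Keep maternal immunization in pregnancy and immunization of the child in infancy as separate answers, and add one for a dose given after infancy, so that every reported history has a place. The added answer only completes the list and implies no view on any schedule. Report the result as ever/never by route, and do not use the item as current-season RSV under-immunization. State in section D whether RSV or measles is intended, so that the role of this item is clear.

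The cost is one reworded question, one added answer and one line on reporting. The study would no longer claim current-season RSV status, which the present item cannot give at these ages. If enrolment has begun, answers collected under the present wording should be reported separately, because their 'No' category cannot be repaired afterwards.

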**C. SUBJECT POPULATION (WHO, WHAT, WHERE)**

Aim 1: Guardians of patients 1 year to 6 years old presenting to the pediatric emergency department 6/1/2025 and 6/1/2026 will be eligible. I expect that we will enroll ~800 parental encounters here at AMC. Parents of children meeting the above inclusion and exclusion criteria will be approached for consent to participate in the study by convenience sampling weekdays 0900-1700. All consenting guardians will complete a brief survey to assess parental demographics and child immunization history. All participants who identify that their child is under-immunized for measles (i.e. did not receive 1st MMR immunization at 1 year of age OR 2nd MMR immunization at 4 years of age) will go on to complete a comprehensive survey to assess immunization beliefs.

Aim 2: In a private location, research assistants (RA) will randomly sample patients between 1 and 6 years of age in the pediatric ED and approach the patient's caregivers for participation in the survey if

eligible. Caregivers will give written consent to participate in the survey. Caregivers will complete this survey in the ED on a private tablet. All guardians who complete the comprehensive survey will be randomized to receive one of four patient-centered immunization messages. The guardian will then be asked again if they plan to immunize their child against RSV this season and if they would accept the immunization if we administer it at the current visit.

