### **Patient recruitment, enrollment, and progress through the study**

Once a patient is screened and determined to be eligible, the RA will review the patient's ED electronic health record (dashboard or face sheet) and record (on a redcap database) the following de-identified information: race/ethnicity, gender, ESI level, insurance status, and chief complaints. [Please see data collection form/survey for further details collected.]

Collecting de-identified data from patient's charts poses no or minimal risk to the patient and it is generally considered acceptable to do this without previously consenting patients. We will keep this information on all patients, even if they refuse to participate in the survey portion, as this information is helpful to understand who are the patients that refused to participate in the study and who are the patients who did participate in the study to comment on the potential sampling bias. These demographic data are (a) de-identified, (b) readily available, (c) can be collected as a chart review without individual patient consent, (d) are not sensitive information, and (e) for patients who do not want to participate in the survey, are not linked in any way with the study questions. The information collected allows the investigators to compare the demographics of participants and non-participants; and therefore, to ensure that the sample is not biased.

If a patient meets the inclusion criteria, a RA will administer the consent for collection of their name, medical record number, and survey responses.

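### Measles under-immunization controls entry to the belief survey and to randomization, but no listed question measures it and its definition ignores the child's current age

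*Protocol*

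**What the plan says.** Eligibility in B. STUDY DESIGN covers "Parents of patients aged 1 year up to and including 6 years of age". The brief survey is introduced with "The below questions will be included in the brief survey". Its immunization-status items are one pooled question, "Is your child up to date with all routine (Not including influenza, COVID-19, RSV) immunizations at this time", and separate questions on influenza, COVID-19 and RSV, the last worded "Is your child immunized against RSV for this season".

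The gate follows: "All participants who identify that their child is under-immunized for measles" continue to the comprehensive survey. A parenthesis explains under-immunized as a first MMR not received at 1 year of age or a second not received at 4 years. Section C. SUBJECT POPULATION repeats the rule in the same form, ending "MMR immunization at 4 years of age) will go on to complete a comprehensive survey to assess immunization beliefs".

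The gate also fixes the trial population, because under Aim 2 "All guardians who complete the comprehensive survey will be randomized to receive one of four patient-centered immunization messages".

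**The concern.** One variable defines both the group whose characteristics Aim 1 is to identify and the population that Aim 2 randomizes. The protocol has two problems with it.

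1. **Measurement.** The listed questions do not collect the variable. A negative answer to the pooled routine-vaccine item does not show that MMR is the missing vaccine.
2. **Definition.** The rule ties each dose to a fixed age and does not ask whether the child has reached that age, or whether a missed dose was given later.

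In Aim 1, children not overdue for MMR could be counted as under-immunized. The error would vary with child's age, because the literal rule itself depends on age, and child's age is one of the factors the analysis is to examine. In Aim 2, guardians outside the target group would be randomized. Messages are assigned after the gate, so this dilutes the population without biasing the comparison between messages.

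**Working it through.** The protocol has no figure of its own to reproduce on this point. The check compares the gate with the data that the protocol says will be collected, then applies the definition to each eligible age.

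**Step 1: is the gating variable collected?**

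| Source in the protocol | Vaccine content | Measles or MMR named? |
|---|---|---|
| Brief survey, item 1 | All routine vaccines, pooled | No |
| Brief survey, item 2 | Influenza | No |
| Brief survey, item 3 | COVID-19 | No |
| Brief survey, item 4 | RSV | No |
| Chart items (Patient recruitment, enrollment, and progress through the study): "race/ethnicity, gender, ESI level, insurance status, and chief complaints" | None | No |
| D. DATA ANALYSIS, data to be collected | Guardian-reported status, in general terms | No |

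Of the 4 listed status items, 0 ask about measles or MMR. Intent to vaccinate against measles is asked in the comprehensive survey, which comes after the gate.

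**Step 2: whom does the literal definition flag?** Eligible single-year ages are 1, 2, 3, 4, 5 and 6, so 6 ages. Take an on-schedule child (dose 1 at age 1, dose 2 at age 4) and a late starter who is now complete (for example dose 1 at age 2, dose 2 at age 5).

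| Child | Current age | Literal rule | Doses received against doses due |
|---|---|---|---|
| On schedule | 1, 2, 3 | Flagged: no second dose at 4 years | Not flagged |
| On schedule | 4 (once dosed), 5, 6 | Not flagged | Not flagged |
| Late but complete | 5 (once dosed), 6 | Flagged: no first dose at 1 year | Not flagged |

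The literal rule flags on-schedule children at 3 of 6 ages. At 2 of 6 ages (1 and 4) the text also does not say when within that year a missing dose starts to count.

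**Step 3: how many children could this be?** This cannot be computed from the protocol. The following is an illustration only. It assumes that 800 guardians enrol, that the general childhood rate r of 8-20% from A. STUDY BACKGROUND AND PURPOSE applies to MMR at every age, that a share s of the children are under 4 (the protocol gives none), and that the literal rule is applied to all of them.

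- Gate limited to doses due: 800 × r = 64 to 160 guardians.
- Literal gate: 800s + 800(1 − s)r. With s = 50%, this is 400 + 32 = 432 at r = 8% and 400 + 80 = 480 at r = 20%.
- Share of those admitted who are not overdue: 800s(1 − r) divided by the literal total. With s = 50%, this is 368/432 = 85% and 320/480 = 67%.
- With s from 40% to 60%, that share runs from 256/416 = 62% to 441.6/505.6 = 87%.

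These figures show that the two readings could describe very different populations. They do not estimate what will happen.

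**The case against.** The strongest reply is that neither error need occur in practice.

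- **The question may exist.** The brief-survey list is not said to be complete, and the protocol refers to a data collection form that we have not seen. Asking guardians to identify a child by named MMR doses presupposes some question about them. The protocol also never says that the pooled item is the gate.
- **Due ages were probably meant.** The parenthesis explains the word under-immunized, and a dose missed at 4 years most naturally presupposes a child who has reached 4. A guardian of an on-schedule 2-year-old would not ordinarily call that child under-immunized. Child's age is collected, so an age-conditioned rule can be applied.
- **Aim 2 is largely protected.** Misclassification precedes randomization, and baseline intent is asked before the message, so guardians who already intend to vaccinate can be identified.

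Much of this stands. It makes the harm conditional and rules out a claim of bias between messages. It does not remove the defect. The protocol spells out separate questions for three other vaccines and omits the one on which entry depends. Nothing tells guardians or research assistants how to class a 2-year-old with one dose or a late completer. A statistical analysis plan could not repair this later, because it cannot recover MMR data that were never asked. Under G. CONFIDENTIALITY the link to the medical record lasts until the master key is destroyed, so status might be checked before then, but no such check is described.

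**Conclusion.** The concern holds, as a correction that should be made. As written, the protocol does not provide for measuring the variable that admits guardians to the comprehensive survey and to randomization: 0 of the 4 listed status items cover it. Its definition, taken literally, misclassifies on-schedule children at 3 of the 6 eligible ages, together with late but complete children.

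Actual misclassification depends on two facts outside the text: whether the unseen form asks MMR status, and whether due ages are applied. If both are so, neither error arises. If not, the consequences are a misclassified Aim 1 group, above all by child's age, and a diluted Aim 2 population. The conclusion does not rest on the illustrative shares in the working.

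**What to change.** 1. Add one item to the brief survey: *How many measles (MMR) doses has your child received: 0, 1, 2 or unsure?* If the data collection form already has such an item, list it in the protocol.
2. Name that item as the gate to the comprehensive survey.
3. In both B. STUDY DESIGN and C. SUBJECT POPULATION, define under-immunized as fewer doses received to date than are due at the child's current age under the protocol's own stated dose ages, whatever the age at which they were given.
4. State whether a missing dose counts from reaching the stated age or from the end of that year of age (this matters only at ages 1 and 4), and how an unsure answer is handled.
5. Use this single variable for both the gate and the Aim 1 classification.

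The cost is one extra question per guardian, one definition sentence in two places, branching on child's age (already collected), and an unsure category to handle.
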